## 5.5 Adverse Events and Other Safety Aspects

### 5.5.1 Definition of Adverse Events

An AE is any untoward medical occurrence in a subject administered a study drug, and which does not necessarily have to have a causal relationship with this treatment. An AE can therefore be any unfavorable and unintended sign (including an abnormal laboratory finding), symptom, or disease (new or exacerbated) temporally associated with the use of a medicinal product whether or not considered related to the medicinal product.

In order to identify any events that may be associated with study procedures and could lead to a change in the conduct of the study, Astellas collects AEs even if the subject has not received study drug treatment. AE collection begins after the signing of the informed consent for the double-blind period and will be collected until 30 days after the last dose of study drug (including the double-blind period and open-label phase if applicable), or initiation of a new therapy for prostate cancer, or the subject is determined to be a screen failure, whichever occurs first. During the post treatment follow-up period, only symptomatic skeletal events need to be reported.

Care will be taken not to introduce bias when detecting AEs and/or SAEs. Open-ended and non-leading verbal questioning of the subject is the preferred method to inquire about AE occurrences.

Some sites may have additional local requirements for events that are required to be reported as AEs or in an expedited manner similar to a SAE. In these cases, it is the investigator's responsibility to ensure these AEs or other reporting requirements are followed and the information is appropriately recorded in the electronic case report form (eCRF) accordingly.

An abnormality identified during a medical test (e.g., laboratory parameter, vital sign, ECG data, physical examination) should be defined as an AE only if the abnormality meets 1 of the following criteria:

- Induces clinical signs or symptoms;
- Requires active intervention;
- Requires interruption or discontinuation of study medication;
- The abnormality or investigational value is clinically significant in the opinion of the investigator.

- CONFIDENTIAL -

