5.2 Safety Population

The safety (SAF) population is defined as all randomized subjects who received at least 1 dose of study drug. The safety population will be used to conduct safety analyses by treatment arm as treated (i.e., based on the actual study drug the subject mostly received, rather than the study drug to which the subject was randomized). The safety population will be used to conduct safety analyses.

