6.2 Safety Variables

Safety will be assessed by evaluation of the following variables:

- Treatment-emergent AEs (TEAEs; frequency, severity, seriousness, and relationship to study drug).
- Clinical laboratory variables (hematology, biochemistry, PSA and testosterone)
- Vital signs (systolic and diastolic blood pressure and pulse rate) and weight
- 12-lead ECG

Treatment-Emergent Adverse Event (TEAE)

A TEAE is defined as an AE that occurs or worsens at any time during the treatment emergent period. The treatment emergent period for double-blind treatment period is defined as the time interval from the first study drug intake up to 30 days after the date of the last dose of study drug, study discontinuation, the start of new antineoplastic therapy or prior to first open-label treatment, whichever occurs first. The treatment emergent period for open-label phase is defined as the time interval from the first open-label study drug intake up to 30 days after the date of the last dose of study drug, study discontinuation or the start of new antineoplastic therapy, whichever occurs first.

If AE start date is the same date as the study start, then it will be considered as a TEAE if the box '*Onset after first dose of study drug taken*' is ticked in the Electronic case report form(eCRF). If a patient experiences an event both during the pre-investigational period and during the investigational period, the event will be considered as TEAE only if it has worsened in severity (i.e. it is reported with a new start date and an increased NCI-CTCAE grade).

AE with both a missing start and stop dates, and AEs with a missing start date but has a known stop date which is on or after the first dose of study drug will be considered treatment-emergent.

AEs will be coded to SOC and preferred term using MedDRA v23.0 (or later version) and severity graded using National Cancer Institute's Common Terminology Criteria version 4.03 (NCI-CTCAE v4.03) for AEs.

Drug-Related TEAE

A drug related TEAE is defined as any TEAE with a causal relationship to study drug as assessed by the investigator in the eCRF (by answering 'YES') or with missing assessment of the causal relationship.

AEs of Special Interest

AEs of special interest are defined in Table 7

Table 7 Selection Criteria for AEs of Special Interest

Event of special interest	Selection based on MedDRA 23.0
Convulsion	Narrow SMQ of 'Convulsions'
Hypertension	Narrow SMQ 'Hypertension'

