Second primary malignancies	
Narrow SMQs of 'Malignant or unspecified tumours' customized to exclude preferred terms of 'Congenital fibrosarcoma', 'Congenital malignant neoplasm', 'Congenital retinoblastoma', 'Metastases to...', 'Metastasis', 'Metastatic neoplasm', 'Prostate cancer...', 'Carcinoid tumour of the prostate', and 'Neoplasm prostate'
 
AND (inclusive of)
 
Narrow SMQ of 'Myelodysplastic syndrome'
 
AND (inclusive of)
 
All preferred terms under High Level Term of 'Myeloproliferative disorders (excl leukaemias)'
 
 Note: Non-melanoma skin cancers are excluded (preferred terms of 'Basal cell carcinoma', 'Basosquamous carcinoma', 'Basosquamous carcinoma of skin', 'Keratoacanthoma', 'Skin cancer', 'Skin cancer metastatic', 'Squamous cell carcinoma', 'Squamous cell carcinoma of skin', 'Lip squamous cell carcinoma')
 
 Note: Those selected SPM cases will be adjudicated by medical review, which will confirm the evidence of a second primary malignancy

Note: Second primary malignancy reported as TEAEs of special interest will be presented for the entire duration of the study, not merely for the treatment-emergent period.

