7 STATISTICAL METHODOLOGY

7.1 General Considerations

For continuous variables, descriptive statistics will include the number of patients (n), mean, standard deviation, median, minimum and maximum. When needed, the use of other percentiles (e.g.10%, 25%, 75% and 90%) will be mentioned in the relevant section.

Frequencies and percentages will be displayed for categorical data. Unless otherwise specified, percentages by categories will be based on the number of patients with no missing data, i.e. will add up to 100%.

All summary tables and figures will be presented by treatment arm and overall for double-blind treatment period, unless stated otherwise. For open-label phase, only selected summaries will be presented , the titles of selected tables, listings and figures for open-label phase summaries will be written out to indicate the “Open-label Phase”, refer to Appendix 3 for detailed analyses for open-label phase. All listings will be produced by site and patient id numbers in ascending order.

Disposition, demographics and other baseline characteristics as well as efficacy data will summarized based on the ITT population, unless stated otherwise. Safety analysis summary and other summaries based on SAF are presented by actual treatment received, unless stated otherwise.

All statistical comparisons will be made using two sided tests comparing double-blind enzalutamide to double-blind placebo. All null hypotheses will be of no treatment difference. All analyses will be based on IRT captured strata. Multiplicity adjustment was incorporated within the interim and final analysis of the primary endpoint according to the O’Brien-Fleming method with a Lan-DeMets alpha spending function (refer to Section 6.1.1.1). And no adjustment for multiplicity will be made for this study on the other endpoints, hence any p-values displayed for those endpoints are intended to be read descriptively.

All data processing, summarization, and analyses will be performed using SAS® Version 9.1.3 or higher. Specifications for table, figures, and data listing formats can be found in the TLF specifications for this study.

For the definition of subgroups of interest, please refer to Section 7.9.

A data analysis cut-off date for the database will be used. All data from visits or assessments done prior to the cut-off date will be reported.

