7.5.1 Adverse Events

The coding dictionary for this study will be MedDRA v23.0. Treatment-emergent AEs will be coded to SOC and preferred terms using MedDRA and graded using NCI-CTCAE v4.03.

Treatment-emergent AEs will be tabulated alphabetically by SOC and by preferred terms within SOC.

An overview table will include the following details per treatment group and overall:

- Number of TEAEs,
- Number and percentage of patients with TEAEs,
- Number of NCI-CTC grades 3 and 4 TEAEs,
- Number and percentage of patients with NCI-CTC grades 3 and 4 TEAEs,
- Number of drug related NCI-CTC grades 3 and 4 TEAEs,
- Number and percentage of patients with drug related NCI-CTC grades 3 and 4 TEAEs,
- Number of drug related TEAEs,
- Number and percentage of patients with causally drug related TEAEs,
- Number of serious TEAEs,
- Number and percentage of patients with serious TEAEs,
- Number of serious drug related TEAEs,
- Number and percentage of patients with serious drug related TEAEs,
- Number of TEAEs leading to death,

- Number and percentage of patients with TEAEs leading to death,
- Number of drug related TEAEs leading to death,
- Number and percentage of patients with drug related TEAEs leading to death,
- Number of TEAEs leading to withdrawal of treatment,
- Number and percentage of patients with TEAEs leading to withdrawal of treatment,
- Number of TEAEs leading to dose reduction,
- Number and percentage of patients with TEAEs leading to dose reduction,
- Number of TEAEs leading to dose interruption,
- Number and percentage of patients with TEAEs leading to dose interruption,
- Number of drug related TEAEs leading to withdrawal of treatment,
- Number and percentage of patients with drug related TEAEs leading to withdrawal of treatment.

An overview table of the TEAE of interest will describe by the number and percentage of patients with TEAEs of interest per treatment group and overall.

The number and percentage of patients with TEAEs, as classified by SOC and preferred terms will be summarized for each treatment group and overall. Summaries will be provided for:

- TEAEs
- NCI-CTC grade 3 or higher TEAEs
- drug related NCI-CTC grade 3 or higher TEAE
- drug related TEAEs,
- serious TEAEs,
- drug related serious TEAEs,
- TEAEs leading to withdrawal of treatment,
- TEAEs leading to dose reduction,
- TEAEs leading to dose interruption,
- drug related TEAEs leading to withdrawal of treatment,

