10.3 Appendix 3 - Statistical Methods for Open-Label Phase

An open-label phase data summary will be presented for subjects who switched treatment from placebo + ADT to enzalutamide + ADT. Data collected in the open-label phase will only be summarized by descriptive statistics unless otherwise specified.

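### Second primary malignancies are shown for the whole study with no rule for cases that start on open-label enzalutamide in placebo crossovers

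*SAP*

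**What the plan says.** SAP 6.2 ends the double-blind treatment-emergent period 30 days after the last dose, or at study discontinuation, "the start of new antineoplastic therapy or prior to first open-label treatment, whichever occurs first". Open-label treatment has its own treatment-emergent period.

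The note under Table 7 in the same section makes one exception. Second primary malignancies "will be presented for the entire duration of the study, not merely for the treatment-emergent period".

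SAP 7.5.1 plans an overview table giving the "number and percentage of patients with TEAEs of interest per treatment group and overall". SAP 7.1 sets the default: "All summary tables and figures will be presented by treatment arm and overall for double-blind treatment period, unless stated otherwise".

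SAP 5.2 assigns safety groups as treated, "based on the actual study drug the subject mostly received, rather than the study drug to which the subject was randomized". It does not say whether open-label dosing counts.

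SAP Appendix 3 adds a separate output: "An open-label phase data summary will be presented for subjects who switched treatment from placebo + ADT to enzalutamide + ADT".

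Protocol 5.5.1 collects adverse events through the open-label phase up to 30 days after its last dose. In post-treatment follow-up it requires only symptomatic skeletal events to be reported.

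**The concern.** Crossover is part of the design. Protocol 12.10 offers open-label enzalutamide to placebo patients after confirmed radiographic progression, before any study-wide unblinding. The stop at first open-label dose is what keeps their later events out of the by-arm safety tables. The Table 7 note removes that stop for second primary malignancies and puts nothing in its place.

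Second primary malignancy is one of the SAP's events of special interest. If enzalutamide did raise the risk, booking on-enzalutamide cases under placebo would pull the comparison towards no difference, which is the less safe direction for a harm. With few cases, one or two in the wrong column could decide how the table reads.

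**Working it through.** The documents give no figure for second primary malignancies, so there is no plan figure to reproduce. The check sets the rules side by side and then illustrates what is at stake.

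**Where does an open-label-onset case go?**

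1. Under the treatment-emergent rule alone, it is outside the double-blind tables.
2. The Table 7 note takes this class out of that rule.
3. The double-blind default in SAP 7.1 gives way where the SAP states otherwise, and the note does state otherwise on the time window.
4. The overview table in SAP 7.5.1 has treatment groups and an overall column, but none for crossovers.
5. Appendix 3 reports open-label events separately, but nothing removes them from a whole-study row elsewhere.
6. The group label comes from SAP 5.2. A crossover who stays labelled placebo brings the case to the placebo column. If the rule counts both phases and his open-label exposure is longer, he moves to the enzalutamide group with his placebo time.

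**Weight of one case.** The planned arms are 120 and 60 (Protocol 7.1). One case in the placebo column adds 1/60 = 1.7 percentage points. One case in the enzalutamide column adds 1/120 = 0.8.

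**Illustration of the placebo-column route.** Assumptions, none of them in the documents: 1 malignancy per 100 patient-years off enzalutamide; true rate ratio 2; a share f = 20–60% of placebo patients cross over; open-label time L = 0.5–1.5 years. Double-blind exposure is set at 17.9 and 7.1 months. These are the pooled phase 3 medians in Protocol 1.3, from other trials, used here as fixed times.

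- Enzalutamide: 1 − exp(−0.02 × 17.9/12) = 2.94%.
- Placebo, cut at first open-label dose: 1 − exp(−0.01 × 7.1/12) = 0.59%.
- Placebo, open-label onsets included: (1 − f) × 0.59% + f × [1 − exp(−0.01 × (7.1/12 + 2L))].
  - f = 0.2, L = 0.5: 0.8 × 0.59 + 0.2 × 1.58 = 0.79%.
  - f = 0.6, L = 1.5: 0.4 × 0.59 + 0.6 × 3.53 = 2.35%.
- The ratio of percentages falls from 4.98 to between 3.73 and 1.25.
- The placebo rate per 100 patient-years becomes (0.592 + 2fL)/(0.592 + fL), which is 1.14 to 1.60. The rate ratio is then 2/1.14 = 1.75 down to 2/1.60 = 1.25, instead of 2.0.
- Expected placebo cases rise from 60 × 0.0059 = 0.35 to between 0.47 and 1.41.

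**With no true effect.** Set the rate ratio to 1 in the same formulas. The enzalutamide percentage is 1.48%. The placebo percentage rises from 0.59% to between 0.69% (0.8 × 0.59 + 0.2 × 1.09) and 1.48% (0.4 × 0.59 + 0.6 × 2.07). The rate ratio stays at 1. So the percentages shift through longer ascertainment in crossovers alone, which is why rates with matching denominators are needed.

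**The two routes are alternatives.** A second illustration simulates the placebo arm. It assumes exponential time to radiographic progression with median 14 or 20 months, uniform accrual over 15 months, cut-off at month 27 or 40, crossing probability 0.5 or 0.8, and exponential open-label stay with median 9 months. Then 24–64% of placebo patients cross over, and a share s = 11–27% of placebo-arm dosing time is open-label. At a true ratio of 2 the observed ratio is 2/(1 + s), about 1.6–1.8. On the same assumptions 10–27% of placebo patients have more open-label than blinded exposure, and they hold 65–71% of the open-label time. If SAP 5.2 moves them, s falls to about 4–12% and the ratio to about 1.8–1.9, before counting the placebo time they carry into the other group. The two effects therefore cannot be added.

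**The case against.** The note changes a time window. It does not mention arms or the open-label phase, and it assigns no case to placebo. Other parts of the SAP lean towards separation: SAP 7.1 frames comparisons as double-blind against double-blind and gives open-label outputs their own titles, and Appendix 3 gives switchers their own adverse event summary. The as-treated rule, "based on the actual study drug the subject mostly received", is most naturally meant for dispensing errors. The events-of-interest table reports numbers and percentages, so a diluted rate ratio matches no planned output. The documents also state no excess risk: second primary malignancy is not among the important identified risks in Protocol 1.4 or the events of special interest in Protocol 1.3. Selected cases are medically adjudicated and all adverse events are listed, so onset could be compared with first open-label dose case by case.

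Most of this stands as a limit on size and certainty. A reader might infer that the SAP does count open-label malignancies against placebo. It does not say so; attribution is simply undefined. A reader might also infer a known dilution, such as 2 seen as 1.6–1.8, but every input to that figure is assumed. What does not stand is the view that separation is already secured. A whole-study window in a by-arm table is a stated instruction, and the separate open-label summary does not undo it. Listings allow a later correction but leave the table ambiguous.

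**Conclusion.** The gap is real but modest. Followed as written, the plan can place on-enzalutamide malignancies of placebo crossovers in the placebo column, or can move long-exposed crossovers and their placebo time to the enzalutamide group. Either blurs the contrast. The firm figure is 1.7 percentage points per case with 60 placebo patients. Any rate dilution needs a true excess risk and crossovers before the data cut-off, and its size cannot be derived from the documents; the ranges shown are illustrations only. Few cases are expected, the table is descriptive, and no efficacy or type I error statement is affected. Label: cheap improvement.

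**What to change.** 1. In the Table 7 note (SAP 6.2), keep the long window but cut the by-arm comparison at first open-label dose. Show cases with onset on or after that dose in a separate open-label enzalutamide column.
2. Give rates per 100 patient-years for each period, with denominators covering the time in which these events were collected. The existing rate in SAP 7.5.1 divides by treatment-emergent time and would not match a whole-study count.
3. In SAP 5.2, after *mostly received*, add that this means during the double-blind treatment period.

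Cost: two SAP clauses and one extra column. Onset dates and first open-label dose dates are already collected, so no new data are needed. The SAP allows revision until database hard lock.

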6.3 Exploratory Endpoint

Not applicable.

6.4 Other Variables

Previous, Concomitant, and Post-treatment Medication or Non-Medication

Previous medications or non-medications are defined as prostate cancer (PC) or non-PC related medications or non-medications taken within 28 days prior to the screening visit and up to the first dose of study.

Concomitant medications or non-medications are defined as PC or non-PC related medication or non-medication with at least one dose taken between the date of first dose (inclusive) and up to 30-day safety follow-up visit after study drug ended.

Post-treatment medication or non-medication are defined as PC or non-PC related medication or non-medication with at least one dose taken after the date of last dose (inclusive) after study drug ended.

A medication or non-medication can be both flagged as previous and concomitant, or both flagged as concomitant and post-treatment.

Dose Reduction and Interruption

During the study, patients who experience a NCI-CTCAE (version 4.03) grade 3 or higher AE (except liver function test AE) that is attributed to the study drug and cannot be ameliorated by the use of adequate medical intervention and/or dose reduction, may interrupt study drug for 1 week or until the toxicity grade improves to grade 2 or lower in severity. Study drug may be restarted at the original dose (160 mg/day) or a reduced dose (120 mg or 80 mg/day) in consultation with the Medical Monitor. After dose reduction, based on patient tolerance, study drug may be increased to a maximum dose of 160 mg/day per Investigator discretion.

Enzalutamide must be interrupted during the evaluation of symptoms suspicious of PRES (headache, lethargy, confusion, blindness and other visual and neurological disturbances, with or without associated hypertension).

Restarting treatment at a reduced dose or after treatment interruption for > 2 weeks must be discussed with the Medical Monitor.

The total number of dose reduction and the total number of interruption will be calculated.

Duration of Exposure

The length of time on treatment will be calculated in days and in months.

For patients who discontinued treatment prior to the data analysis cut-off date

Duration of exposure (months) = [(date last dose of study - date of first dose) + 1] / 30.4375

For patients who did not discontinue treatment prior to the data analysis cut-off date

Duration of exposure (months) = [(data cut-off date - date of first dose) + 1] / 30.4375

Average Daily Dose

The average daily dose is based on the actual dose taken while taking into account dose reduction and dose interruption periods as recorded in the dosing page of the eCRF. The average daily dose is;

The cumulative dose

Duration of exposure (in days)

where the cumulative dose is defined as the sum of all daily dose actually taken.

Percent Overall Compliance (compared to the theoretical full dose of 160 mg/day)

Percent overall compliance is based on the drug accountability data as recorded in the IVRS system.

Percent overall compliance is defined as the total number of capsules taken divided by the total number of capsules that should have been taken:

$$\frac{[\text{Total number of capsules consumed}]}{[(\text{'Date last study drug returned'} - \text{'Date first dose'}) + 1] \times 4} \times 100$$

The total number of capsules consumed will be calculated based on the number of capsules dispensed at all study visits minus the number of capsules indicated as returned, from the kits returned. The kits dispensed at the last visit for patients still on treatment by the data analysis cut-off date and for which the number of capsules returned is unknown will not be considered.

Refer to Appendix 2 - Adjustments in Calculation of Dose Compliance Details on the calculations for dose compliance.

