7.3.2 Treatment Compliance

Percent overall compliance with the dosing schedule will be examined on drug accountability data for patients in the SAF for whom, at least a kit was returned and the first and last days of treatment (or the patient still on treatment by the cut-off date) are known.

Percent overall compliance will be summarized as follows:

- Descriptive statistics will be presented by treatment group and overall.
- Percent compliance will be categorized according to the following categories:
 - less than or equal to 70%
 - greater than 70%, less than or equal to 90%
 - greater than 90%, less than or equal to 110%
 - greater than 110%
 - Unknown.

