10.2 Appendix 2 - Adjustments in Calculation of Dose Compliance Details

The steps described below are used for the calculation of the **cumulative dose** based on the drug accountability data. The calculation of the **cumulative dose** based on the dose records in eCRF is not covered in this appendix.

By protocol, the dispensed kits should be returned at the next scheduled visit, but that may not always happen in reality and for some patients the kits may be returned later or not all returned. The protocol study visits are scheduled at equal time intervals. Patients who are ongoing treatment by the time of data cut-off may have not returned all the dispensed kits and some patients may return all or some of the treatment kits after the end of treatment date.

The following general rules apply to the calculation of percent dose compliance:

1. Percent dose compliance should not be calculated for kits not returned, or for which the number of capsules returned are unknown, or returned on the same day or earlier than dispensed
2. Percent dose compliance calculations should be based on treatment kits returned
3. Every kit dispensed should have a total of X capsules, where X=number of capsules that should be taken per day*number of days until next refill. In this study, this number should be 124 (4 capsules per day*31 days) at week 1 day 1 visit and all treatment period visits thereafter.

The aim is to calculate a running sum of the drug dose at each visit where kit/s is/are dispensed, while adjusting the calculation for time interval between visits, time returned and the time of return in regards to end of treatment date. The cumulative dose is then used to calculate the percent overall compliance using the formula specified in Section 6.4.

I. For patients with kits returned prior to the end of treatment

1. At week 1 day 1 visit
 - Patients receive one kit only (1 bottle of 124 capsules)
 - It is possible that patients forget to return their kit at the next visit and bring it at a later visit than planned
 - 124 capsules is maximum 31 days of treatment which is more than the 28 days planned between visits
 - the last day of any period will be added to the first kit taken, therefore 1 is added
 - ➔ So, the theoretical cumulative number of capsules used between day 1 and week 5 for a kit returned prior to the end of treatment is:
 $4 * (date\ of\ return - start\ date) + 1\ or\ 31\ at\ most$
2. At week 5 visit and every visit thereafter

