 - patients receive 1 kit
 - It is possible patients forget to return their kit at the next visit, as requested by protocol, and bring it at a later visit or even after treatment ended

- The treatment can also end during the use of the kit (but it will be assumed that the drug will then be returned after end of treatment for at least one kit or on that day at the earliest)
- 124 capsules is maximum 31 days of treatment
- ➔ So, *per kit*, for kits returned prior to the end of treatment, the theoretical number of capsules between 2 of the 4-weekly visits, to add to the cumulative number, is:
4((date of return - date of dispense) or 31 at most)*

II. For patients with kits returned on or after end of treatment

The following points should be considered when going through the steps outlined below:

- It is possible that some patients return their kits (some or all of them) after end of treatment (i.e. kits were dispensed before end of treatment and then returned after end of treatment)
- In theory for patients who end treatment there should always be at least one kit returned on or after the end of treatment date
- In these cases the date the kit/s was/were returned should not be considered and the end of treatment date should be used instead
- Such cases would be the last ones to consider in the calculation of the cumulative dose

1. At week 1 day 1 visit

- Patients receive one kit only (1 bottle of 124 capsules)
- It is possible patients forget to return their kits at the next visit and instead bring them after EOT despite that they might have continued with treatment for a much longer time
- 124 capsules is maximum 31 days of treatment which is more than the 28 days planned with next visit
- The last day of any period will be added to the first kit taken => +1 is added
- ➔ So, the cumulative theoretical number of capsules between day 1 and week 5 for kit returned after the end of treatment, is:
4 ((date of end of treatment - start date) +1 or 31 at most)*

2. During 2 consecutive 4-weekly visit

- Patients receive 1 kit
- It is possible patients forget to return their kits at the next visit and instead bring them after EOT despite that they might have continued with treatment for a much longer time
- 124 capsules is maximum 31 days of treatment
- ➔ So, the theoretical cumulative number of capsules between those 2 consecutive 4-weekly visits is:
4((date of end of treatment - dispense date) or 31 at most)*

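### The percent-compliance denominator in SAP 6.4 runs to the last drug-return date, against its own definition and Appendix 2, and can understate compliance after treatment stops

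*SAP*

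**What the plan says.** **SAP 6.4, Percent Overall Compliance.** The measure is "the total number of capsules taken divided by the total number of capsules that should have been taken". The denominator as printed is four times the number of days, inclusive, from first dose to "Date last study drug returned". The numerator is "the number of capsules dispensed at all study visits minus the number of capsules indicated as returned, from the kits returned". The section ends with a pointer: "Refer to Appendix 2 - Adjustments in Calculation of Dose Compliance Details on the calculations for dose compliance".

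**SAP Appendix 2, general rules.** "Percent dose compliance should not be calculated for kits not returned, or for which the number of capsules returned are unknown"; the calculation rests on returned kits. The appendix builds a running capsule total kit by kit, from dates only, and closes the loop: "The cumulative dose is then used to calculate the percent overall compliance using the formula specified in Section 6.4".

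**SAP Appendix 2, part II** (kits returned on or after end of treatment). "In these cases the date the kit/s was/were returned should not be considered and the end of treatment date should be used instead". It adds that, in theory, every patient who ends treatment has at least one such kit.

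**SAP 7.3.2.** Compliance is summarised in the safety population, overall and in bands, one of which is "greater than 70%, less than or equal to 90" per cent. The band above it runs from over 90% to 110%.

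**The concern.** The denominator is meant to be the capsules that were due. None are due after the last dose, so each day between last dose and final return is counted as four missed capsules. The same section ends duration of exposure at the last dose for patients who discontinued, so exposure and compliance would use different end dates for the same patient.

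The two sections refer to each other without settling the matter. Section 6.4 calls Appendix 2 an adjustment, and Appendix 2 returns its result to the 6.4 formula. That result is labelled both a cumulative dose, which suggests a numerator, and a theoretical number of capsules, which suggests a denominator. Two programmers could reasonably produce different tables.

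What is at stake is the accuracy of the compliance table and its bands. Because the understatement grows as exposure shortens, an arm whose patients stop earlier could show lower compliance with no difference in pill-taking.

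**Working it through.** **The one stated number.** Appendix 2 gives 124 capsules per kit: 4 × 31 = 124. This reproduces. The SAP states no compliance percentage to check.

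**Inputs.** Dose of 4 capsules a day and the date rules: SAP 6.4 and Appendix 2. Bands: SAP 7.3.2. The delay d from last dose to last return is not stated. Protocol 5.1.4 says only that unused drug comes back at visits. The next scheduled visit after the last dose is the safety follow-up at 30 days, window ±7, so 23 to 37 days (or sooner, if new therapy starts). I take d = 0, 7, 23, 30 and 37 as an assumed range.

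**Section 6.4 read literally.** First dose on day 1, last dose on day T, last kit returned on day T+d, every capsule taken:

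compliance = 4T / {4 × [(T+d−1)+1]} = T/(T+d)

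| T (days) | d=0 | d=7 | d=23 | d=30 | d=37 |
|---|---|---|---|---|---|
| 28 | 100% | 80.0% | 54.9% | 48.3% | 43.1% |
| 84 | 100% | 92.3% | 78.5% | 73.7% | 69.4% |
| 168 | 100% | 96.0% | 88.0% | 84.8% | 82.0% |
| 270 | 100% | 97.5% | 92.2% | 90.0% | 87.9% |
| 365 | 100% | 98.1% | 94.1% | 92.4% | 90.8% |
| 730 | 100% | 99.1% | 96.9% | 96.1% | 95.2% |

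**When the band changes.** T/(T+d) ≤ 0.90 requires T ≤ 9d: 63, 207, 270 or 333 days for d = 7, 23, 30 or 37. T/(T+d) ≤ 0.70 requires T ≤ (0.7/0.3)d: 16, 53, 70 or 86 days.

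**Appendix 2 total, T=84, visits every 28 days.** Kit 1: 4 × (28+1) = 116. Kit 2: 4 × 28 = 112. Kit 3, to end of treatment: 4 × (84−57) = 108. Sum = 336 = 4 × 84, the capsules due. (This assumes kits 1 and 2 come back at the next visit; one returned late is charged up to 31 days, 124 capsules instead of 112.)

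- As the denominator: 336/336 = 100%, whatever d is.
- As the numerator over the 6.4 denominator with d=30: 336/(4 × 114) = 73.7%, the same understatement. It would also not measure intake, because the total contains no count of returned capsules.

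**Unreturned kits.** Take three 28-day kits, full adherence, and a numerator limited to returned kits.

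- Second kit missing, third returned on the last-dose day: 4 × 56 / (4 × 84) = 224/336 = 66.7%.
- Third kit missing: the last return is on day 57, so 224/(4 × 57) = 224/228 = 98.2%.

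**Possible arm effect, illustration only.** Protocol 1.3 gives pooled phase 3 median exposures of 17.9 months on enzalutamide and 7.1 on placebo. At 30.4375 days a month these are 544.8 and 216.1 days. With full adherence and d=30: 544.8/574.8 = 94.8% and 216.1/246.1 = 87.8%. With d=7: 98.7% and 96.9%. Four of those five studies were in castration-resistant disease, so the medians need not carry over.

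**The case against.** The best defence is that the plan already contains the cure. Section 6.4 defines the denominator correctly in words and sends the reader straight to Appendix 2, whose title calls it an adjustment. Appendix 2 discards the late return date, calls its totals theoretical and leaves out unreturned kits. Applied as an override of the denominator, it removes both problems. That is a fair account of the likely intent. It fails as a full answer because Appendix 2 labels its result a cumulative dose and returns it to a 6.4 formula whose printed denominator it never changes.

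Three further objections stand and limit the point:

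- A reader might infer that fully compliant patients who stop are generally reported as poor compliers. The documents do not support that. It needs a late final return and fairly short treatment. Appendix 2 says only that some patients may return kits after end of treatment, and a same-day return gives no error.
- A reader might infer that any unreturned kit pulls a patient down to about two thirds. Only a missing non-final kit does so.
- A reader might infer a certain bias between arms. Treatment runs to radiographic progression, and no expected treatment duration is given for this trial. A patient stopping at the assumed placebo PSA-progression median of 9 months (274 days), with d=30, scores 274/304 = 90.1% and stays in the upper band.

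**Conclusion.** The conflict is real, and the formula as printed gives a wrong figure whenever the last kit comes back after the last dose. The error is always downward. It is nil for same-day return and, at one year or more on treatment, under 10 percentage points even with d=37. It is material for short treatment: about 26 points at 84 days with d=30. A fully adherent patient drops to 90% or below only if treated for at most 63, 207, 270 or 333 days with d = 7, 23, 30 or 37.

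These sizes rest on an assumed return delay and on a literal reading of 6.4. A difference between arms is possible, not established. The reach is limited to the descriptive compliance table: no efficacy analysis or analysis set in the SAP uses this percentage, and exposure and average daily dose come separately from the dosing records, which allows a cross-check.

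**What to change.** In SAP 6.4:

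- End the denominator at the earlier of the last dose (end of treatment) date and the last return date.
- For patients still on treatment, use the last return on or before the data cut-off. Do not use the cut-off itself: 6.4 leaves the capsules of the last, unreturned kit out of the numerator, so running to the cut-off would add days with no matching capsules and bring the same bias back.
- Count only days covered by kits with known returns.
- State that the Appendix 2 theoretical total is the denominator, and that capsules dispensed minus capsules returned, from those same kits, is the numerator.

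In Appendix 2, check the bracket in I.1 against II.1 in the source file. As extracted, I.1 adds 1 after multiplying by 4, whereas II.1 adds it before. For a 28-day interval that is 4 × 28 + 1 = 113 against 4 × 29 = 116. The asterisks in these formulas are displaced, so the difference may be a PDF artefact.

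The cost is a few lines of SAP wording and a small programming change. No data collection or efficacy analysis is affected.
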